The overall purpose of this protocol is to assess the biomechanical and neurophysiologic effects of rehabilitative strategies and protocols that are commonly used during physical therapy treatment of gait disorders post-stroke. As part of this protocol, 45 able-bodied individuals and 55 individuals with chronic stroke will be assigned to either Cohort 1 or Cohort 2, and will participate in 1-18 gait training sessions. If interested, study participants can also complete both study cohorts sequentially (with at least 3-weeks duration between switching from one cohort to the second). Evaluations for obtaining outcome measures will comprise clinical testing, muscle evaluations, gait analysis, and assessment of spinal and corticospinal excitability. Within Cohort 1 (stroke and able-bodied), 25 subjects will receive identical treatment throughout the training sessions (i.e. FastFES training). Within Cohort 2, 25 subjects will receive different rehabilitation strategies individually or in combination during each training session (e.g., treadmill walking, functional electrical stimulation, bio-feedback or verbal feedback about targeted walking parameters, split-belt walking, etc.). During gait training, Cohort 1 subjects will typically participate in a minimum of 2 and a maximum of 3 sessions per week. Subjects in Cohort 2 can participate in 1 to 18 gait training sessions but the frequency of the gait sessions can be varied according to the subject's and laboratory schedule (i.e. variable durations between consecutive sessions).

Aims

The aims of this protocol are to:

- 1) Study the changes in gait biomechanics, corticospinal excitability, and walking function during 18 sessions of gait retraining (Cohort 1).
- 2) Systematically determine the effect of parameters such as walking speed (slow, fast, variable, split-belt walking), functional electrical stimulation parameters (short-term changes induced by fast versus FastFES, stimulation intensity, number of muscles stimulated), and bio-

[figure not shown]
feedback on within-session changes in gait biomechanics, walking function, and corticospinal excitability (Cohort 2).

Hypotheses of the study

- By utilizing data collected on cohort 1 of subjects who undergo 18 sessions of FastFES gait retraining, the following hypothesis will be tested:

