 - H1.* Eighteen sessions (6-8 weeks) of gait training comprising fast treadmill walking and functional electrical stimulation (FastFES) will result in Improvements in gait biomechanics, corticospinal excitability, and walking function.
 - H2.* Improvements in gait biomechanics will precede the improvements in corticospinal excitability and walking function.
 - H3.* Improvements in walking function will be correlated to improvements in corticospinal excitability.
- By utilizing data collected on cohort 2 of subjects who receive different rehabilitation strategies during each training session, we will analyze short-term changes induced by 1-3 sessions of gait retraining to test the following hypothesis:
 - H4.* The magnitude of improvements in gait biomechanics and corticospinal excitability will be greater for gait training sessions that comprise:
 - walking at a faster versus slower speed
 - walking with versus without FES, i.e. Fast versus FastFES
 - walking with FES delivered to two versus one muscle during gait
 - walking with 2 belts going at different speeds or directions versus regular treadmill walking
 - walking with versus without visual bio-feedback or other feedback (e.g. verbal, tactile) about targeted parameters during gait
 - greater dosages (# of walking steps per session) of walking practice
 - combination of 2 strategies versus a single rehabilitation strategy

5. Study design and methods

Research Procedures

Flowchart showing the overview of study procedures.

The overall goal of this protocol is to provide novel insights into the biomechanical and neural mechanisms underlying gait rehabilitation. To achieve this goal, a series of experiments will be performed on young able-bodied individuals as well as stroke survivors. The protocols to be tested and procedures to be used are described in detail here. For all the procedures and sessions described below, all testing procedures will be explained to the subject at the beginning of each testing session. Also,

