Hypotheses testing will be done with a p-value set at 0.05. The outcome variables used for analyses will include peak knee and ankle flexion during walking, propulsive forces during walking, walking speed and endurance, peak and duration of EMG activation during walking, and TMS-derived measures of corticospinal excitability (peak EMG in response to TMS, motor threshold intensity, slope and peak of the TMS-recruitment curve). To test *H1*, for each of the variables, one-way repeated measures ANOVA will be performed to check for differences in the variable after versus before 18 sessions of training. To test *H2*, we will plot the dependent variable versus time (test session number). Using these plots, the time to plateau and the time when the variable first shows a positive within-session change (threshold time) will be determined. One way repeated measures ANOVA will be used to compare the time to plateau and threshold time among 3 variables – peak propulsion, peak TMS muscle response, and over ground walking speed. To test *H3*, a Pearson's correlation will be performed between the change in peak propulsion after training versus change in peak TMS muscle response after training. For the hypothesis involving within-session changes (*H4*), repeated measures ANOVA will be performed to compare the within-session percentage change for each variable between different rehabilitation strategies.

Power Analysis: The current protocol has been powered using the primary outcome measure of paretic propulsive force generation. Based on means and standard deviations from our existing pilot data, for each aim, a sample of 24 subjects will provide 80% power to detect a 4.2% difference in propulsive force between sessions with standard deviation of 6% at a two-sided alpha level of 0.05. After completion, the data from this study will be used to conduct systematic power analysis for other outcome variables, which will be utilized to design a larger-scale future study.

8. Adverse event reporting

We will notify the IRB of any adverse events that occur during the protocol.

10. Device information

Equipment for Motion Analysis and Gait Retraining: A 7-camera system will be used to collect motion analysis data (Vicon, Oxford, UK). Ground reaction forces during treadmill walking will be collected using a treadmill instrumented with two 6-component force platforms under each

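### The 80% power claimed for each aim is not shown for Aim 2: H4 has seven contrasts, none of them primary, and no fixed number of participants completing both conditions of any of them

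*Combined protocol and SAP*

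**What the plan says.** The Power Analysis paragraph of Section 7 says that the protocol is "powered using the primary outcome measure of paretic propulsive force generation" and that "for each aim, a sample of 24 subjects will provide 80% power to detect a 4.2% difference in propulsive force between sessions". The inputs it gives for this are an SD of 6% and two-sided testing at 0.05. For testing in general, Section 7 says "Hypotheses testing will be done with a p-value set at 0.05". It gives no multiplicity rule. H4 is to be analysed by repeated measures ANOVA on within-session percentage change, compared between strategies.

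Aim 2 is carried by H4 in Section 4. H4 lists seven contrasts: speed, FES, two muscles versus one, split-belt, feedback, dose, and combined versus single strategies. None is named as primary. The data for H4 are described as "short-term changes induced by 1-3 sessions of gait retraining".

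On who supplies the data, Section 4 says: "Within Cohort 2, 25 subjects will receive different rehabilitation strategies individually or in combination during each training session". The same section lets a Cohort 2 subject attend between 1 and 18 sessions at a flexible frequency. Section 5 (Research Procedures) permits, but does not require, cross-over between strategies, within a session or across sessions. Section 5 (Procedures for Gait Training Sessions) refers to a different type of training at each of 18 sessions. It also singles out Hypothesis 4b, FastFES versus Fast, as informing the sample size of a later, larger trial. Section 6 expects about 10% withdrawal.

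**The concern.** A power figure for a paired comparison depends on the number of people who complete both members of the pair. Section 7 supplies that number, 24, as if it applied to Aim 2 as a whole. But Aim 2 has seven comparisons, and no section says how many Cohort 2 subjects will complete both conditions of any of them. A subject who attends once, with no cross-over inside that session, contributes to none. Allocation follows what is scheduled, and nothing in the text directs 24 people, or any other minimum, to a given contrast.

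At stake is how the results are read. A non-significant strategy contrast based on a handful of pairs would sit under a protocol statement of 80% power and could be taken as evidence of no useful difference. For 4b this matters further, because its data are meant to help size the next trial. A second gap is that seven contrasts are tested at 0.05 with no primary contrast and no alpha rule, so the plan does not say what power or error rate applies to Aim 2 as a family.

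**Working it through.** **Inputs.** From Section 7: difference 4.2%, SD 6%, two-sided alpha 0.05, n = 24, stated power 80%. From Section 4: seven H4 contrasts and 25 Cohort 2 subjects. From Section 6: about 10% withdrawal.

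**Method.** The analysis is within-subject, so a two-condition contrast is a paired t-test. With d = difference / SD of paired differences, power is the probability that a noncentral t with n − 1 degrees of freedom and noncentrality d√n exceeds the two-sided critical value.

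**Step 1: the plan's own figure.** Read 6% as the SD of paired differences (the text does not say). Then d = 4.2/6 = 0.70. With n = 24 the noncentrality is 0.70 × √24 = 3.43, the critical value is 2.07, and power is 90.7%. The stated 80% is not reproduced, but on this reading it is conservative: 18 pairs give 79.9% and 19 give 82.3%.

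If 6% is instead a per-session SD, the SD of differences is 6√(2(1 − ρ)), where ρ is the correlation between sessions. Power at n = 24 is then 64.2% for ρ = 0, 79.3% for ρ = 0.30 and 90.7% for ρ = 0.50. Reproducing 80% takes ρ of about 0.31, which the plan does not state.

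**Step 2: power by number of complete pairs** (d = 0.70, unadjusted 0.05).

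| Complete pairs | Noncentrality 0.70√n | Power |
|---|---|---|
| 24 | 3.43 | 91% |
| 22 | 3.28 | 88% |
| 19 | 3.05 | 82% |
| 11 | 2.32 | 55% |
| 10 | 2.21 | 51% |
| 7 | 1.85 | 34% |
| 4 | 1.40 | 17% |
| 3 | 1.21 | 11% |

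The 22 is 25 × 0.9 = 22.5, rounded down. It applies if 25 is the enrolled number and all 25 are stroke participants.

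**Step 3: how the small numbers could arise.** Assume that the 25 subjects are spread evenly over the seven contrasts; the documents do not say this.
- One contrast each: 25 × 1/7 = 3.6, so 3-4 pairs and 11-17% power.
- Two each: 25 × 2/7 = 7.1, so about 7 pairs and 34% power.
- Three each: 25 × 3/7 = 10.7, so 10-11 pairs and 51-55% power.

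For comparison, 19 pairs in every contrast need 7 × 19 = 133 person-contrasts, or 133/25 = 5.3 per person.

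**Step 4: multiplicity with full attendance.** Suppose all 24 complete every contrast. Bonferroni over seven sets alpha at 0.05/7 = 0.00714, the critical value rises to 2.95, and power per contrast is 68%; 80% then needs 30 pairs. Without adjustment, seven independent tests at 0.05 carry a family-wise error of 1 − 0.95⁷ = 30.2%. Independence is an assumption; the upper bound is 7 × 0.05 = 35%.

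**The case against.** The strongest reply is that nothing in the design prevents the claimed power. H4 is a within-subject comparison, and using the same people for several contrasts does not reduce the power of any one of them. If 24 people complete a pair, power is about 91% on the SD-of-differences reading, better than claimed, and 19 would do. Up to 18 sessions per person, plus cross-over inside a session, leave room for all seven contrasts. The protocol also singles out 4b, which suggests that effort may be concentrated there rather than spread evenly.

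Much of this stands. A reader might infer that the 80% is simply false for Aim 2, because the analysed exposure is 1-3 sessions per person and each person can therefore feed only about two contrasts. The documents do not support that. The phrase "short-term changes induced by 1-3 sessions of gait retraining" may mean 1-3 sessions per strategy rather than per person, and the session limit and cross-over rule allow one person to serve many contrasts. Even three sessions can yield more than two contrasts: slow, Fast and FastFES sessions give speed and FES, and Fast versus FastFES arguably also serves the combination contrast.

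A reader might also infer that all seven contrasts feed the sample size of the future trial. In Section 5 only Cohort 1 and 4b are named for that.

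What the reply does not supply is a number. Attendance may be a single session, cross-over is optional, and no minimum number of completers is set for any contrast, 4b included. Nor does full attendance answer the question of seven tests with no primary contrast.

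**Conclusion.** The concern holds as a gap in support, not as a demonstrated shortfall. The 80% in Section 7 is a property of one contrast with a known number of complete pairs. For Aim 2 neither the contrast nor the number is specified, so the claim is not established for any H4 contrast or for H4 as a family.

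Achieved power could lie anywhere from about 11% (3 pairs) to about 91% (24 pairs), and at 68% with 24 pairs under Bonferroni. These figures rest on 6% being the SD of paired differences; the lower ones also rest on an even split over seven contrasts, which is illustrative. If 6% is a per-session SD with low correlation, every figure is lower.

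Two further points bear on the 24. The powered outcome is paretic propulsion, which only stroke participants can supply, and Section 4 does not say that all 25 Cohort 2 subjects are stroke participants. Withdrawal of about 10% would leave about 22 of 25. The study is not invalidated, but the power statement should be corrected.

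**What to change.** In Section 7:
- Limit the Aim 2 power statement to one prespecified contrast, FastFES versus Fast (H4b), on paretic propulsion in stroke participants. The protocol already relies on this contrast to plan the later trial.
- Schedule both 4b conditions for every Cohort 2 stroke participant, and state the minimum number of completers: about 19 for 80% power if 6% is the SD of paired differences.
- State whether 6% is that SD. If it is a per-session SD, give the assumed correlation and recompute the minimum.
- State how many Cohort 2 subjects are stroke participants, and restate power for the completers expected after about 10% withdrawal (about 88% with 22).
- Label the other six contrasts exploratory, each reported with its own n and 95% confidence interval and with no power claim. With one confirmatory contrast, Aim 2 needs no multiplicity adjustment for H4 on the primary outcome.

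The cost is protocol wording, the scheduling of two conditions per participant, and fewer sessions left for the exploratory contrasts. Whether extra participants are needed depends on how many of the 25 are stroke participants, which the protocol should state first.
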